7.1.3 Systemic/Topical Treatment at Study Entry

If a subject is receiving systemic corticosteroids or immunosuppressants, or topical steroids to control uveitis prior to study enrollment, that subject will have such treatment ended within three months following study Day 1, in a manner that follows the standard of care for ending the specific treatment. For example, some systemic treatment regimens may be ended immediately, while others require a period of gradual dose reduction (tapering). Systemic medications or topical steroids administered as part of gradual dose reductions are not considered prohibited medications. Medications received as such treatments will not be recorded on the concomitant medications page but will be recorded on a separate eCRF page.

The number and percentages of subjects with at least one systemic/topical treatment medication at the time of study entry will be summarized by treatment group. The number and percentages of all medications received as systemic/topical treatments will be summarized by treatment group and by ATC level 1 term, ATC level 2 term, and preferred term. All summaries will be performed using the Safety population.

7.2. Ocular Surgeries

All ocular surgeries, including cataract removal, during a subject's participation in the study will be recorded on the eCRF. The number and percentage of subjects with at least one surgery/procedure and at least one surgery/procedure for each of the specified reasons (recurrence of uveitis, treatment emergent AE, increased IOP, cataract, other) will be summarized by treatment group and eye (study, fellow). A frequency distribution for the number of surgeries/procedures during the study per subject will also be presented. All summaries will be performed using the Safety population and percentages will be based on the total number of subjects in the Safety population.

Ocular surgery data, including details on the procedure, eye, study eye designation, start date, and reason for the surgery, will be presented in a listing.

7.2.1 Surgical Intervention to Control Elevated IOP

The number and percentage of subjects requiring any surgical intervention to control elevated IOP will be summarized by treatment group, eye (study, fellow), and time interval. Ocular surgeries with a reason of "Increased IOP" will be included in the summary. Incidence will be summarized overall through 6 months and for 6 month time intervals through 12 (or 36) months.

A summary of incidence of surgical interventions to control elevated IOP will also be presented by geographic region (United States, EMEA, and India) and history of incisional surgery to control elevated IOP (History of Incisional Surgery, No History of Incisional Surgery). All summaries will be performed using the Safety population.

A listing of all subjects requiring surgical interventions to control elevated IOP will be provided. This listing will include details relating to the IOP-lowering surgical intervention (procedure, eye, study eye designation, and date procedure performed), demographic and baseline ocular

characteristics including BCVA and IOP, the last available BCVA and IOP values as of the data cut-off, and the date of first recurrence of uveitis, if any.

7.2.2 Cataract Surgeries

The number and percentage of subjects requiring cataract surgery will be summarized by treatment group, eye (study, fellow), and time interval. Only eyes which are indicated as phakic at study entry will be included for analysis. Ocular surgeries with a reason of “Cataract” will be included in the summary. Incidence will be summarized overall through 6 months and for 6 month time intervals through 12 (or 36) months. All summaries will be performed using the Safety population and percentages will be based on the total number of phakic eyes in the Safety population.

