A higher incidence of anemia (irrespective of relationship to drug) was observed in subjects who received Iluvien compared to sham (3%, sham; 7%, 0.2 μg FA /day; 9%, 0.5 μg FA /day). The cause of this increase is not known and was not considered by the Data Monitoring Safety Board to be related to FA. It has been hypothesized that the increase may be due to the use of oral carbonic anhydrase inhibitors (CAIs) (which occurred more frequently in the active treatment groups). This class of IOP-lowering drugs is known to exacerbate renal dysfunction and possibly compromise erythropoietin production. A post-hoc analysis was performed in which all subjects were categorized with or without anemia and with or without a systemic CAI (administered during or within 90 days of anemia). Based on a Pearson chi-square test, there was a relationship between the use of a CAI and anemia in the 0.2 μg FA /day group (p-value <0.0001, and in the 0.5 μg FA /day group (p=0.0073).

Deaths and Serious Adverse Events

A total of 56 (6%) deaths were reported in the FAME studies. None of the deaths were attributed to study drug or unexpected in the patient population.

A total of 401 (42%) subjects had at least 1 drug-related serious adverse event (SAE), all of which were ocular in nature. The overall incidence of drug-related SAEs was several-fold higher in the Iluvien insert groups relative to sham.

Ocular Adverse Events

In the FAME Studies, the most common drug-related TEAEs were cataract operation (39% of subjects), cataract (36%), increased intraocular pressure (25%), and myodesopsia (8%).

Cataract-Related Events in Phakic Subjects

The FAME studies enrolled 621 subjects with phakic study eyes at baseline; the remaining 335 study eyes were pseudophakic at baseline. The incidence of cataract in the study eye was higher in the active treatment groups [80% (low dose), 88% (high dose)] than in the sham group (46%). The most common types of cataracts in the study eye were cataract (NOS) and posterior subcapsular cataract, both of which were reported more frequently in the active treatment groups than in the sham group. The percentage of phakic subjects who had a cataract operation in the study eye was also higher in the active treatment groups [75% (low dose), 85% (high dose)] than in the sham group (23%).

IOP-Related Events and Procedures

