Continuous data will be described using descriptive statistics (i.e. n, mean, standard deviation, median, minimum, and maximum). Categorical data will be described using the subject count and percentage in each category. For the summary statistics of all numerical variables unless otherwise specified, minimum and maximum will be displayed to the same level of precision as reported. Mean and median will be displayed to one level of precision greater than the data collected. Standard deviation / standard error will be displayed to two levels of precision greater than the data collected. P-values will be rounded to three decimal places. If a p-value is less than 0.001 it will be reported as “<0.001.” If a p-value is greater than 0.999 it will be reported as “>0.999.” Data will be displayed in all listings sorted by treatment group.

Subjects will be identified in the listings by the subject identification number concatenated with the investigator number.

When count data are presented, the percentage will be suppressed when the count is zero in order to draw attention to the non-zero counts. A row denoted “Missing” will be included in count tabulations where specified on the shells to account for dropouts and missing values. The denominator for all percentages will be the number of subjects in that treatment within the analysis population of interest, unless otherwise specified.

Unless otherwise specified, baseline will be defined as the last non-missing evaluation prior to or on the date of treatment injection (Day 1). The study day will be calculated as assessment date – date of treatment injection (Day 1) + 1.

For all efficacy and safety analyses, analysis visit windows will be used for assigning assessments to an analysis visit, as follows:

| Scheduled Visit | Target Day | Visit Window (Days) |
|-----------------|------------|---------------------|
| Screening | -30 to -1 | Not applicable |
| Day 1 | 1 | Not applicable |
| Day 7 | 7 | 5 to 9 |
| Day 28 | 28 | 25 to 31 |
| Month 2 | 60 | 53 to 67 |
| Month 3 | 90 | 83 to 97 |
| Month 6 | 180 | 152 to 208 |
| Month 9 | 270 | 242 to 298 |
| Month 12 | 360 | 332 to 388 |
| Month 18 | 540 | 512 to 568 |
| Month 24 | 720 | 692 to 748 |
| Month 30 | 900 | 872 to 928 |
| Month 36 | 1080 | 1052 to 1108 |

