Only those assessments which are assigned to an analysis visit will be included in the summary tables and figures which are presented by visit. For summaries of an event at or before a given time point, such as recurrence at Month 12, all assessments (including unscheduled visits) on or before the upper limit of the corresponding visit window will be considered. All assessments will be presented in the data listings.

For summaries presented by 3 month time intervals through Month 12, the intervals will be defined based on study days and the analysis visit windows, as follows:

- Day 1 to 3 months: day 1 to day 97 (upper limit of Month 3 visit window)
- 3 to 6 months: day 98 to day 208 (upper limit of Month 6 visit window)
- 6 to 9 months: day 209 to day 298 (upper limit of Month 9 visit window)
- 9 to 12 months: day 299 to day 388 (upper limit of Month 12 visit window)

For summaries presented by 6 month time intervals, the intervals will be defined based on study days and the analysis visit windows, as follows:

- Day 1 to 6 months: day 1 to day 208 (upper limit of Month 6 visit window)
- 6 to 12 months: day 209 to day 388 (upper limit of Month 12 visit window)

- 12 to 18 months: day 389 to day 568 (upper limit of Month 18 visit window)
- 18 to 24 months: day 569 to day 748 (upper limit of Month 24 visit window)
- 24 to 30 months: day 749 to day 928 (upper limit of Month 30 visit window)
- 30 to 36 months: day 929 to day 1108 (upper limit of Month 36 visit window)

The Month 6 analysis will include all assessments (events, medications, etc.) with a start day on or before the upper limit of the Month 6 visit window (study day 208). The Month 12 analysis will include all assessments (events, medications, etc.) with a start day on or before the upper limit of the Month 12 visit window (study day 388). The analysis at Month 36 will include all data in the database.

For tabulations of data on the Safety population, subjects who were randomized but did not receive treatment will not be included; however data for all subjects in the Safety population will be included in the data listings. In the listings, subjects who did not receive treatment will be grouped separately by their randomized treatment assignment (i.e., FAI Insert - Not Treated, Sham Injection - Not Treated). Percentages for Safety population summaries will be based on the total number of subjects who receive treatment.

All analyses will be conducted using SAS Version 9.2 or higher.

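### The cataract-surgery table by 6-month interval divides by all eyes phakic at entry throughout, so it understates late risk among eyes still at risk, more so in the insert arm

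*SAP*

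**What the plan says.** SAP 7.2.2 (Cataract Surgeries) sets who is counted: "Only eyes which are indicated as phakic at study entry will be included for analysis". It sets the denominator: "percentages will be based on the total number of phakic eyes in the Safety population". Its time axis is worded as in SAP 7.2.1: "Incidence will be summarized overall through 6 months and for 6 month time intervals through 12 (or 36) months". Nothing in 7.2.2 removes an eye from the denominator once it has been operated on or its subject is no longer followed.

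The general rules in SAP Section 4 do not do so either. By default the "denominator for all percentages will be the number of subjects in that treatment within the analysis population of interest", and for safety tables "Percentages for Safety population summaries will be based on the total number of subjects who receive treatment". Kaplan-Meier estimation is planned in SAP 8.2 for time to recurrence of uveitis, but not for surgery.

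SAP 7.2 plans a study-long percentage of subjects with at least one procedure for each reason, cataract included. Its denominator is the whole Safety population, so eyes that were never phakic dilute it. For phakic eyes, 7.2.2 states an overall figure only through 6 months.

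For IOP surgery, SAP 7.2.1 counts "The number and percentage of subjects requiring any surgical intervention to control elevated IOP", and "All summaries will be performed using the Safety population". It gives no denominator of its own, so the Section 4 rule applies.

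**The concern.** Restricting the table to phakic eyes makes sense because an eye without its natural lens cannot need cataract surgery. The same is true of an eye operated on at Month 8 when the 12 to 18 month interval is tabulated. The plan applies the restriction once, at entry, and never updates it.

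SAP 3.2 names cataract-related procedures as a safety endpoint, and the insert is meant to release drug for 36 months, so how surgical risk moves over that time is a real safety question. Someone reading incidence by interval will tend to take each percentage as the risk in that interval. Depletion is faster in the arm with more surgery, so the understatement differs between arms and flatters the insert.

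**Working it through.** The plan gives no figure for this table. Its only design calculation, 89% power for the primary test, reproduces (0.892 from the continuity-corrected formula at 40 and 80 subjects), but nothing here depends on it.

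**Inputs.** Protocol 5.3.2.2.2 says of the 36-month diabetic macular edema studies: "The percentage of phakic subjects who had a cataract operation in the study eye was also higher in the active treatment groups". The figures are 75% for the low-dose insert, which Protocol 5.3.2.2 calls virtually the same product, and 23% for sham. The documents do not give the timing of these operations or the expected loss to follow-up, so both are assumed below. The six intervals are treated as equal. In SAP Section 4 the first runs 208 days and the others 180, which is ignored here.

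**Constant hazard, no loss.** Let F be the 36-month rate. The risk per interval among unoperated eyes is h = 1 − (1 − F)^(1/6).

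- Insert: h = 1 − 0.25^(1/6) = 20.6%
- Sham: h = 1 − 0.77^(1/6) = 4.3%

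The percentage tabulated for interval j with the fixed denominator is (1 − h)^(j − 1) × h.

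| Months | Insert eyes still unoperated at start | Insert, tabulated | Sham, tabulated | Ratio | Difference (points) |
|---|---|---|---|---|---|
| 0–6 | 100% | 20.6% | 4.3% | 4.84 | 16.4 |
| 6–12 | 79.4% | 16.4% | 4.1% | 4.01 | 12.3 |
| 12–18 | 63.0% | 13.0% | 3.9% | 3.33 | 9.1 |
| 18–24 | 50.0% | 10.3% | 3.7% | 2.76 | 6.6 |
| 24–30 | 39.7% | 8.2% | 3.6% | 2.29 | 4.6 |
| 30–36 | 31.5% | 6.5% | 3.4% | 1.90 | 3.1 |

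With an at-risk denominator every row would read 20.6% against 4.3%, a ratio of 4.84. The fixed-denominator insert column sums to 75%.

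**Adding 20% drop-out by Month 36 (assumed).** The monthly hazards in the insert arm are λ = −ln(0.25)/36 = 0.0385 for surgery and δ = −ln(0.80)/36 = 0.0062 for loss.

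- Sum of the insert intervals: λ/(λ + δ) × (1 − 0.25 × 0.80) = 0.861 × 0.80 = 69%, against a true 75%.
- Last insert interval: exp(−30(λ + δ)) × λ/(λ + δ) × (1 − exp(−6(λ + δ))) = 0.2615 × 0.861 × 0.235 = 5.3%.
- If loss happens only at interval ends, the sum is 70.1% and the last interval 5.4%. On that basis 10% loss gives a sum of 72.6% and 30% loss 67.5%.

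**Rising hazard, same 75% total, no loss.** With the hazard rising linearly, at-risk percentages are 6.4, 12.4, 18.0, 23.2, 28.1 and 32.7. The fixed denominator shows 6.4, 11.6, 14.7, 15.6, 14.5 and 12.1. The tabulated series rises to Month 24 and then turns down, and the last interval shows 12.1% where the at-risk figure is 32.7%.

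**IOP surgery, for comparison.** Protocol Table 2 gives 4.8% at 36 months for the low-dose insert, or 1 − 0.952^(1/6) = 0.82% per interval. If only first operations counted, the last interval would show 0.78%. If repeat operations count, as the wording of 7.2.1 allows, there is no decline without loss. With 10% to 30% loss and repeats counted, the last interval is 0.92 to 0.74 of the first.

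**The case against.** The strongest reply is that the fixed denominator is a legitimate quantity. Without loss, first-surgery percentages over all entry-phakic eyes are increments of cumulative incidence. They sum to 75% and 23%, and they compare the arms on a set defined at baseline. An at-risk denominator conditions on what happened after randomisation. If eyes differ in susceptibility, the insert arm's later risk set is selectively depleted, so its interval ratios are not neutral either. This stands, and it is why the existing percentages should be kept and supplemented. It does not cover loss to follow-up, which makes even the sum too low.

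The plan also has partial remedies. SAP 7.2 gives a study-long percentage per reason and a listing with surgery dates, and SAP 7.3.1 bands the duration of participation. A reader could recover much of the follow-up from these. They still do not give a cumulative percentage among phakic eyes to Month 36 or a number at risk.

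The numbers will be small. If all 80 insert study eyes were phakic, about 80 × 0.315 = 25 would remain unoperated at Month 30. With 40 sham eyes, 3.4% to 4.3% is fewer than two eyes per interval. The fall in the ratio could not be told from noise in this trial alone, and the input rates come from a different disease.

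A reader might infer that the IOP-surgery and IOP-medication tables (SAP 7.2.1 and 7.1.2.1) share the fault. The documents do not support this. Section 7.2.1 counts any intervention and 7.1.2.1 is not limited to first use, so a subject already treated can be counted again and rightly stays in the denominator. Only loss to follow-up matters there, and nothing in the documents says it will be greater in the insert arm.

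**Conclusion.** The point holds for cataract surgery. The SAP fixes the denominator at eyes phakic on entry, never updates it, and plans no at-risk or censoring-adjusted summary. Late-interval risk among eyes still at risk is therefore understated, more in the arm with more surgery. Under constant hazards matching 75% and 23% and no loss, the last insert interval reads 6.5% where the at-risk risk is 20.6%, and the insert-to-sham ratio drifts from 4.8 to 1.9. With an assumed 20% drop-out, the insert intervals sum to about 69% in place of 75%.

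It would be tempting to say that the table must show the risk waning. That needs a roughly constant or falling hazard, and the protocol gives 36-month totals without timing. Under a rising hazard the tabulated series climbs first, and what remains is the understatement of late risk. The sizes are illustrative. These are descriptive safety tables, and the primary efficacy analysis is unaffected.

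**What to change.** In SAP 7.2.2:

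- Add Kaplan-Meier cumulative incidence of first cataract surgery among entry-phakic eyes, by arm, at Months 6, 12, 18, 24, 30 and 36.
- Keep the interval percentages, and print beside each one the number of eyes still phakic and in follow-up at the start of the interval.

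In SAP 7.2.1 and 7.1.2.1, leave the denominators as they are. At most, show the number of subjects still in follow-up at the start of each interval.

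Surgery dates and last-visit dates are already collected (SAP 7.2 and 7.3.1), so no new data are needed. The cost is a little more programming, and later insert-arm figures that look less favourable.

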7.3. Study Treatments

Fluocinolone acetonide (FA) is the active ingredient in the FAI insert. The FAI insert is provided in a sterile preloaded applicator and is administered via injection through the pars plana with a 25 g needle. The FAI insert contains 0.18 mg FA and delivers FA into the vitreous humor for a period of 36 months.

The sham applicator is an empty 1 mL syringe attached to a blunt needle; it does not contain a FAI insert.

Data related to the study treatment procedure will be presented in a listing.

7.3.1. Extent of Exposure

For subjects in the FAI insert group, overall duration of exposure is defined as the total number of days a subject is exposed to any study drug and will be presented as the total number of days from the injection date (Day 1) to either the FAI insert removal date, for those subjects who have the insert removed while in the study, or the last visit date (date of insert removal or last visit - the date of injection + 1) as recorded on the End of Study/Early Termination page. If the last visit date on the End of Study/Early Termination page is missing, or if a subject is lost to follow-up, the latest available visit date will be used. Duration of exposure at Month 6 is defined similarly to overall exposure, using either the FAI insert removal date, if removal occurred prior to Month 6 visit date, or the Month 6 visit date as the cut off date. If a subject’s Month 6 visit date occurs later than the data cut off for the Month 6 analysis (upper limit of Month 6 visit window) then the upper limit of the Month 6 visit date will be used as the end date of exposure. A similar approach will be used to define duration of exposure at Month 12.

The duration of study participation will be summarized for all subjects. The duration of study participation (days) is calculated as date of last visit as recorded on the End of Study/Early Termination page – date of Day 1 visit + 1. If the last visit date on the End of Study/Early Termination page is missing, or if a subject is lost to follow-up, the latest available visit date will be used. Duration of study participation at Month 6 is calculated as the date of Month 6 visit – date of Day 1 visit + 1. If a subject’s Month 6 visit date occurs later than the data cut off for the Month 6 analysis (upper limit of Month 6 visit window) then the upper limit of the Month 6 visit date will be used as the end date of participation. A similar approach will be used to define duration of study participation at Month 12.

The duration of exposure to study drug and duration of study participation up to Month 6 (or 12 or 36) will be summarized by treatment for all subjects in the Safety population and will be presented in a table by summary statistics. The durations of exposure and study participation will then be classified into one of the following categories: ≤ 28 days, 29 to 60 days, 61 to 90 days, 91 to 180 days, 181 to 270 days, 271 to 360 days, 361 to 540 days, 541 to 720 days, 721 to 900 days, 901 to 1080 days, and ≥ 1081 days and will be presented as the number and percentage of subjects in each duration category. Percentages will be computed from the number of subjects in the Safety population.

A summary of each subject's exposure and duration of study participation will be presented in a listing.

8. Efficacy Analysis

PSV-FAI-001 is intended to support submissions to the US Food and Drug Administration (FDA) and submissions to other regulatory authorities in the rest of the world (ROW). The FDA has requested a definition of recurrence for the primary efficacy analyses that differs from the definition of recurrence in PSV-FAI-001. The recurrence definition to be used for the US/FDA is outlined in [Section 8.1](#) below. The FDA definition of recurrence will also be used for all supporting sensitivity analyses, subgroup analyses, and exploratory analyses on recurrence of uveitis endpoints for the FDA submission.

Efficacy analyses will be performed on both the ITT and PP populations at 6, 12 and 36 months. All primary and exploratory efficacy endpoints will be analyzed using the ITT and PP populations. The ITT analyses will be considered primary; the PP analyses will be considered supportive of the primary analyses on the ITT population.

